7.5.2.3 Overall Survival

Overall survival (OS) is defined as the time from randomization to death due to any cause. Specifically,

$$\text{OS} = \text{Date of death} - \text{Date of randomization} + 1.$$

In the absence of confirmation of death, OS will be censored at the last date the patient is known to be alive. If the last recorded date where a patient is known to be alive is the date of randomization, survival time will be censored on the date of randomization (i.e., OS duration of 1 day).

OS will be analyzed using Kaplan-Meier methodology. The median survival time and its two-sided 90% CI using the log-log transformation method (Collett 1994) will be calculated and presented when appropriate. Kaplan-Meier plots for the two treatment groups will be provided. Additionally, probability of OS will be reported at various time intervals (e.g. every 6 months). The associated two-sided 90% CIs will be calculated.

7.5.2.4 Objective Response Rate (ORR)

ORR is defined as the proportion of patients with CR or PR at the EOT visit according to the Lugano classification criteria (Cheson 2014). Patients whose disease response cannot be assessed per Lugano classification criteria will be scored as Not Evaluable for calculating the ORR.

ORR by IRF and by investigator assessment will be summarized and the corresponding exact two-sided 90% confidence interval using the Clopper-Pearson method (Clopper 1934) will be presented.

7.5.2.5 Duration of Objective Response

Duration of objective response (DOR) is defined as the time from start of the first documentation of OR to the first documentation of PD, new anticancer therapy or to death due to any cause, whichever comes first. Note that receipt of post treatment consolidative radiotherapy, post treatment chemotherapy for the purpose of mobilizing PBSCs, or ASCT will not be considered to have started new anticancer therapy.

DOR will be analyzed in the same methodology as duration of CR as described in Section 7.5.2.2.

7.5.2.6 The Proportion of Patients Achieving Peripheral Blood Stem Cell (PBSC) Mobilization

The proportion of patients achieved PBSC mobilization will be summarized by treatment arm and total using the mITT Analysis Set. The total number of CD34-positive cells mobilized will be summarized. The corresponding exact two-sided 90% confidence interval using the Clopper-Pearson method (Clopper 1934) will be presented. PBSC mobilization collection will be listed for each patient by visit.

7.5.2.7 The Proportion of Patients Receiving Autologous Stem Cell Transplant (ASCT)

The proportion of patients intent to receive and received ASCT will be summarized by treatment arm and total using the mITT Analysis set. The reason for not receiving subsequent stem cell transplant after EOT will be summarized for patients who intended to receive ASCT.

7.5.3 Pharmacokinetics and Immunogenicity Endpoints

7.5.3.1 Pharmacokinetics

The individual plasma concentrations of denintuzumab mafodotin and rituximab will be summarized with descriptive statistics (including geometric mean and coefficient of variation) at each PK sampling timepoint using the Safety Analysis Set. The PK parameters may include, but are not limited to, maximum plasma concentration (C_{max}), area under the plasma concentration-time curve (AUC), and plasma concentrations at trough (C_{trough}). PK data from this study will be analyzed by non-compartmental analysis (NCA) methods. If performed, exploratory PK/pharmacodynamic (PD), PK/safety, or PK/efficacy analyses will be described in a separate analysis plan and the results reported separately from the CSR. Geometric mean ratio estimates and 90% CIs of pharmacokinetic parameters against Cycle 1 will be computed from a log-transformed model for Cycles 2 and beyond. These data may also be combined with data from other studies for population PK (POPPK) and exposure-response analyses through a separate analysis plan and through separate reporting.

7.5.3.2 Antitherapeutic Antibody (ATA) Incidence Rate

The ATA incidence rate is defined as the proportion of patients that develop ATA at any time during the study. ATA incidence will be summarized by visit and overall using the Safety Analysis Set.

7.5.3.3 Pharmacodynamic (PD) and Mechanism of Action Biomarkers

The analyses for pharmacodynamic biomarkers and for biomarkers related to drug mechanism(s) of action will be defined in a separate Biomarker Analysis Plan and may be included in a separate report.

7.6 Safety Analyses

The Safety analysis set will be used to summarize all safety endpoints.

Adverse events will be coded using Medical Dictionary for Regulatory Activities (MedDRA, Version 18.0 or higher).

Laboratory values will be graded according to the National Cancer Institute (NCI) Common Terminology Criteria for Adverse Events (CTCAE version 4.03 or higher).

Concomitant medications will be coded using WHO Drug (version: June 2015 or more recent).

7.6.1 Adverse Events

Adverse events will be summarized by MedDRA preferred term in descending frequency of occurrence unless otherwise specified. For incidence reporting, if a patient reports more than one AE that was coded to the same system organ class or preferred term, the patient will be counted only once for that specific system organ class or preferred term.

A treatment-emergent AE is defined as a newly occurring or worsening AE after the first dose of study treatment. See Appendix B for details regarding treatment-emergent classification. An overall summary of AEs will be provided. Summaries of AEs will also be provided for the following:

- All treatment-emergent AEs
- Serious Adverse Events (SAEs)
- AEs related to study treatment
- SAEs related to study treatment
- AEs leading to dose modification (delay, elimination, reduction, and unplanned adjustments)
- AEs regarded as infusion reactions
- AEs regarded as hypersensitivity reactions
- AEs regarded as protocol-defined “dose delay toxicity” (by cycle and overall)
- AEs leading to treatment discontinuation
- Grade 3 - 5 treatment-emergent AEs
- Treatment-emergent AEs by system organ class, preferred term and maximum severity. At each system organ class or preferred term, multiple occurrences of events within a patient are counted only once at the highest severity
- Treatment-emergent AEs by system organ class and preferred term

All adverse events, serious adverse events, adverse events leading to treatment discontinuation, and adverse events leading to death will be listed.

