3.2.3 Blinding

This study is not blinded.

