6.6 End of Treatment Visit

End of Treatment (EOT) visits should occur 14 to 30 days after the start of the last cycle (administration of denintuzumab mafodotin in the 19A+RICE Arm, or Day 1 of RICE in the control arm), unless delayed due to an AE. However, EOT evaluations must be performed before initiation of a new therapy, inclusive of radiotherapy and ASCT. If EOT evaluations are completed before 30 days after completion of study treatment, the patient will also be contacted 30–37 days following the completion of study treatment to assess for adverse events.

- Physical examination
- Review of inflammatory conditions (only for those patients with certain inflammatory conditions of interest at Screening/Baseline)
- ECOG performance status
- B symptom assessment
- ECG
- Ophthalmology exam (not required if an exam was performed within 4 weeks prior to the EOT visit, and following the last dose of study treatment)
 - Ocular health survey (± 2 days from the ophthalmology exam)
- Pregnancy test for females of childbearing potential
- Serum chemistry panel
- CBC with differential
- PT/PTT/INR
- Spot urine for UPC calculation
 - 24-hour urine collection if UPC > 2 (within 5 days after UPC assessment)
- Blood samples for PK, ATA, and biomarker assessments (see [Table 3](#))
- For patients discontinuing treatment due to disease progression: if a tumor biopsy was performed at the time of disease progression as part of standard of care, submit sample of tumor specimen, if available (see [Section 7.4.4](#))

The following response assessments are required (unless progressive disease [PD] was documented within the previous 6 weeks by diagnostic CT/PET scan):

- CT of diagnostic quality of neck, chest, abdomen, and pelvis (see Section 7.2)
- PET scan (Note: a combined CT/PET may be obtained to satisfy the requirements for CT and PET scanning, as long as the CT is of diagnostic quality)
- If patient is scheduled to undergo stem cell collection and bone marrow biopsy is performed as part of standard of care, record the bone marrow biopsy result for lymphoma involvement in the CRF.

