7.7.1.3 Reporting Periods for Adverse Events and Serious Adverse Events

The safety reporting period for all AEs and SAEs is from study Day 1 (predose) through the EOT visit or 30 days after last study treatment (denintuzumab mafodotin or any component of RICE), whichever is later. However, all study protocol-related AEs are to be recorded from the time of informed consent. All SAEs that occur after the safety reporting period and are considered study treatment-related in the opinion of the investigator should also be reported to the sponsor.

SAEs will be followed until significant changes return to baseline, the event stabilizes (recovering/resolving) or is no longer considered clinically significant by the investigator, or the patient dies or withdraws consent. All non-serious AEs will be followed through the safety reporting period. Certain non-serious AEs of interest may be followed until resolution, return to baseline, or study closure.

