9.3.9.2 Adverse Events

Adverse events will be defined as treatment emergent if they are newly occurring or worsen following study treatment. The incidence of all AEs, treatment-emergent AEs, and treatment-related AEs will be tabulated using the Safety Analysis Set. AEs will be classified by system organ class and preferred term using the Medical Dictionary for Regulatory Activities (MedDRA).

AEs will be listed and summarized by MedDRA preferred term, severity, and relationship to study drug. In the event of multiple occurrences of the same AE with the same preferred term in one patient, the AE will be counted once as the occurrence. AEs leading to premature discontinuation of study drug will be summarized and listed in the same manner.

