Appendix B Definition of the Term “Treatment-Emergent” with Respect to AE Classification

The algorithm below should be used to determine whether an adverse event (AE) is classified as a treatment-emergent adverse event (TEAE). A TEAE is defined as any AE which is newly occurring or worsening in severity, where newly occurring means that the AE was not present at baseline. For ease of reading, both pre-existing conditions and AEs will be referred to as AEs for the remainder of this document. AE dates should be imputed in accordance with the algorithm detailed in Appendix A prior to determination of TEAE classification. Details of the TEAE classification are as follows:

1. Determine the first/earliest dose date of any study treatment (for combination studies this includes any component of the regimen)
2. **Baseline AEs:** classify an AE as a baseline AE if it satisfies both of criteria a and b below:
 - a The onset period field is: “started before the signing of informed consent”; or “started after consent but before the first dose of any study treatment”; or, the onset period field is missing and the AE start date is prior to the first dose date of any study drug (step 1, above).
 - b The stop date satisfies either of i or ii below:
 - i. The stop date is the same as or a later date than the first dose date of any study treatment
 - ii. The stop date is missing with outcome equal to
 - recovering/resolving (this outcome may or may not be associated with a date), or
 - not recovered/not resolved, or
 - unknown.
 - Note: if the AE has no outcome or stop date provided, the CRF data should be queried
 - c Note: If the event ended on Day 1 (the date of first dose of any study drug) it will be considered a baseline event.
3. **Post-baseline AEs:** classify an AE as post-baseline if it meets either of criteria a or b below:
 - a The onset period of the AE is “started after the first dose of any study treatment”
 - b The onset period of the AE is missing and the AE start date is the same as or a later date than the first dose date of any study treatment
4. Compare post-baseline AEs to baseline AEs using the lower level term (LLT) and determine classification. **Note that classification may not be possible and the TEAE variable will be missing:**
 - a Classify all baseline AEs as not treatment emergent (not TEAEs).

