- b If a baseline and post-baseline AE have the same LLT but the post-baseline AE has a greater CTC grade then classify the post-baseline AE as a TEAE. If the post-baseline grade is less than or equal to the baseline grade then the post-baseline AE is not a TEAE.
- c If there are no baseline AEs with a matching LLT for the post-baseline AE then classify the post-baseline AE as a TEAE.
- d If the post-baseline AE is uncoded then classify the post-baseline AE as a TEAE.

NOTE:

1. **For summaries which include only treatment emergent AEs include all AEs which are classified as TEAEs as well as those AEs for which TEAE status could not be determined (e.g., the value of the TEAE variable may be missing if the event cannot be identified as baseline or post-baseline - missing information on the AE CRF should be queried). Only exclude those AEs which were determined to not be treatment emergent.**
2. **Events that have an end date prior to the first dose date (e.g. protocol procedure related events) should be classified as not treatment emergent (not TEAEs).**

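### The SAP gives treatment-emergent AEs a start but no end, so late SAEs collected only if judged treatment-related can enter the by-arm safety tables

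*SAP*

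**What the plan says.** **Definition of treatment-emergent.** SAP 7.6.1: "A treatment-emergent AE is defined as a newly occurring or worsening AE after the first dose of study treatment". SAP Appendix B repeats the idea: "A TEAE is defined as any AE which is newly occurring or worsening in severity". When the onset-period field is missing, its post-baseline rule requires only that "the AE start date is the same as or a later date than the first dose date of any study treatment". For TEAE summaries the closing note of Appendix B instructs: "Only exclude those AEs which were determined to not be treatment emergent". Protocol 9.3.9.2 adds no limit: "Adverse events will be defined as treatment emergent if they are newly occurring or worsen following study treatment".

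**Collection.** Protocol 7.7.1.3 runs the safety reporting period from Day 1 to the later of the EOT visit and 30 days after the last dose of any study treatment. Beyond it, sites owe the sponsor a narrower set: "All SAEs that occur after the safety reporting period and are considered study treatment-related in the opinion of the investigator should also be reported". Protocol 7.7.1.2 has SAEs entered on both the CRF and the SAE form.

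**Presentation.** SAP 6.1 presents summaries by arm and in total. SAP 7.6.1 lists tables of all TEAEs, Grade 3–5 TEAEs, SAEs, related AEs and related SAEs. Only some of these are restricted to treatment-emergent events. On masking, protocol 3.2.3 says: "This study is not blinded".

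**The concern.** A by-arm incidence table is interpretable when events in both arms are found in the same way. Up to the end of the reporting period they are: every AE counts, whatever its cause. After it, an SAE is on record only if an investigator who knows the arm attributes it to study treatment. The SAP rule does not separate the two kinds of event, so a late related SAE is a TEAE on the same footing as a Cycle 1 event.

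The threshold for attribution may differ by arm. Protocol 7.7.1.1 asks for causality against denintuzumab mafodotin and against RICE. A late SAE therefore has two possible attributions in the investigational arm and one in the control arm.

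The counts may also move with the cutoff. Under SAP 6.11 the CR analysis follows EOT, the PFS and OS analysis comes about two years after the last enrolment, and later cutoffs are allowed. Related late SAEs could keep entering throughout.

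Safety of the combination is the first-listed secondary objective and has no formal hypothesis (protocol 9.3.1), so these descriptive tables carry the comparison.

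**Working it through.** The plan states no figure on this point, so there is none to reproduce. The check has two parts.

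**1. Is there an upper bound anywhere?**

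- SAP 7.6.1: lower bound only (first dose).
- SAP Appendix B: lower bound only. Late onset is not a ground for exclusion.
- Protocol 9.3.9.2: none.
- SAP Appendix A: last dose plus 30 days appears, but only to impute AE end dates.
- SAP 7.6.7: deaths are split at 30 days after last treatment. AEs and SAEs have no matching split.

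So no analysis rule closes the window. Only the collection rule does, and it leaves related SAEs open.

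**2. How large could the effect be?** This is an illustration with true SAE risk equal in both arms. None of the inputs is in the documents; all are assumptions except the roughly 50 patients per arm (SAP 6.2).

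- w = risk of an SAE within the reporting period: 30–50%
- q = risk of a first SAE afterwards, among patients without one in the period: 5–30%
- r = chance that the late SAE is called related, as RICE/19A+RICE pairs: 20/20, 20/40, 20/60 and 10/50%

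Recorded proportion = w + (1 − w) × q × r

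Gap between arms = (1 − w) × q × (r₁ − r₀), where r₁ is 19A+RICE and r₀ is RICE

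True proportion = w + (1 − w) × q

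| w | q | r₀ / r₁ | RICE | 19A+RICE | Gap (points) | Patients of 50 | True, both arms |
|---|---|---|---|---|---|---|---|
| 0.30 | 0.30 | 0.2 / 0.6 | 34.2% | 42.6% | 8.4 | 4.2 | 51% |
| 0.30 | 0.20 | 0.2 / 0.4 | 32.8% | 35.6% | 2.8 | 1.4 | 44% |
| 0.50 | 0.05 | 0.2 / 0.4 | 50.5% | 51.0% | 0.5 | 0.25 | 52.5% |
| 0.30 | 0.20 | 0.2 / 0.2 | 32.8% | 32.8% | 0 | 0 | 44% |

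First row in full: 0.30 + 0.70 × 0.30 × 0.2 = 0.342; 0.30 + 0.70 × 0.30 × 0.6 = 0.426; difference 0.084.

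The factor (1 − w) matters, because a patient already counted for an SAE in the period adds nothing to any-SAE incidence. Leaving it out would turn the first row into 0.30 × 0.4 = 12 points.

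With the window closed at the end of the reporting period, the recorded proportion is w in each arm, and the gap is 0 for any q and r.

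**The case against.** **Collection already bounds almost everything.** Protocol 7.7.1.1 has AEs recorded only through the safety reporting period, and the schedule of events agrees. No new non-serious AE is due afterwards. This stands: the issue is confined to late SAEs.

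**A reader might infer that late related SAEs are certain to reach the tables.** The documents do not settle that. Protocol 7.7.1.3 asks for a report to the sponsor, and 7.7.1.4 describes an SAE form sent to Drug Safety. For pregnancies, 7.7.1.2 separates the two routes: Drug Safety for 12 months, the AE CRF for 30 days. Against this, the general instruction in 7.7.1.2 puts SAEs on the CRF and makes no exception for late ones. Entry is likely, not proven.

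**A reader might infer a bias against 19A+RICE.** The direction cannot be derived. Protocol 5.8 calls myelosuppression an expected consequence of RICE, and protocol 1.4 calls haematopoietic toxicity uncommon with denintuzumab mafodotin. A late cytopenia could be put down to RICE in either arm.

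**A reader might add that toxicity of the next therapy is charged to the randomised regimen.** EOT may fall 14 days after the last cycle starts (Day 15, protocol 6.6). With etoposide typically ending on Day 3 (5.3.3), full collection runs to Day 3 + 30 = Day 33, an overlap of up to about 33 − 15 = 18 days. But those events are fully collected by design, and closing the window would not affect them. The design CR rates imply 65% and 40% of patients not in CR, but these are not rates of next-line therapy, since partial responders may also proceed to transplant. At most this supports a supplementary table.

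**Moving late SAEs out could hide serious late ocular events**, which SAP 7.6.1.1 treats as of special importance. This is fair, and it is why the later events need their own by-arm display.

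**Conclusion.** The gap in the definition is real and follows from the text alone: treatment emergence is open-ended, while collection changes in kind at a boundary that the SAP does not use. Late related SAEs can therefore sit in the all-TEAE, Grade 3–5 and SAE tables beside fully collected events.

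A better TEAE definition is not enough on its own. The SAE and related-event tables in SAP 7.6.1 are not limited to TEAEs and need the window stated separately. In the related-SAE table, relatedness is the entry condition anyway, so the distortion falls mainly on the other three.

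The size rests wholly on assumed rates: 0 to 8.4 points over the combinations tried, 0 with equal attribution, and the opposite sign if RICE-arm events were the more readily called related. The primary endpoint is unaffected. The point merits a change because closing the gap costs so little.

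**What to change.** 1. In SAP 7.6.1 and Appendix B, define a TEAE as onset or worsening from first dose through the end of the safety reporting period in protocol 7.7.1.3.
2. State the same window for the SAE, related-AE and related-SAE summaries.
3. Present later related SAEs, including late ocular SAEs, in a separate by-arm summary and listing, so that no safety information is lost.
4. Optionally, add a by-arm TEAE table restricted to events before subsequent anticancer therapy. Do not cut at mobilisation: protocol 5.9 allows it during study treatment, so such a cut could drop on-treatment events.

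The cost is SAP wording, one or two extra tables, and a few late related SAEs moved out of the main tables. Under protocol 9.3 a change in analysis methods needs a protocol amendment only if it alters site conduct, and this one does not. It should be made before database lock.

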7.6.1.1 Adverse Events of Special Importance

Adverse events of ocular AEs will be considered AEs of special importance.

7.6.1.1.1 Ocular AEs

Incidence, onset and improvement/resolution of ocular AEs of interest will be summarized based on the safety analysis set. The ocular AEs of interest will be defined by Standardised MedDRA Queries (SMQs) or Sponsor Specified Queries (SSQs) as appropriate. The

definition of the SSQs will be maintained in a separate document and will be finalized prior to database lock.

Patient incidence of treatment-emergent ocular AEs of interest will be presented by system organ class, preferred term and maximum severity. Ocular AEs leading to treatment discontinuation will be summarized.

Time to onset and duration to improvement or resolution will be summarized at the patient level for ocular AEs.

Date of onset is defined as the date of earliest occurrence of events of interest. Time to onset for will be summarized by descriptive statistics.

Improvement and resolution of ocular AEs will be derived per patient level. The date of resolution is defined as the earliest time that the patient does not have any ongoing ocular events (i.e. all events with outcome of resolved/recovered or resolved/recovered with sequelae, or all events with severity decreasing to baseline condition or better).

Improvement of ocular AEs is defined based on the worst grade for each patient. If a patient has worst grade 3 or 4 events, date of improvement or resolution is defined as the earliest date that the patient does not have any ongoing grade 3 or 4 events (i.e. the worst grade the patient is experiencing is 2 or below). If a patient has worst grade 2 ocular events of interest, the date of improvement or resolution is defined as the earliest date that the patient does not have any ongoing grade 2 events (i.e. the worst grade the patient is experiencing is 1 or below).

Time to improvement and resolution from first onset and from last treatment of 19A will be summarized for the patients who experienced ocular AEs of interest. Duration of ocular AEs may be summarized by Kaplan-Meier methodology. If a patient does not experience an improvement or resolution, the patient will be censored at last contact date for ocular symptoms, and censored at the date of last ophthalmology exam for corneal findings.

The relationship between ocular AEs and ocular interventions may be explored.

